Scenario #2: At the time of disease progression while being treated with a CDK4/6 inhibitor (ribociclib **or** palbociclib **or** abemaciclib)+ AI, tamoxifen or fulvestrant

In scenario #1, the study will provide patients with ribociclib + letrozole, but patients will not be randomized until they demonstrate objective evidence of disease progression on treatment. If the patient has previously received letrozole, an alternative AI can be prescribed but will not be provided by the study, i.e. administered as standard of care (ribociclib and letrozole will still be provided by the study). Patients are allowed to have received 4 consecutive weeks of an aromatase inhibitor prior to protocol registration for scenario 1. In scenario #2, patients will be randomized after registration.

At randomization, patients will be assigned to one of the two arms in a 1:1 ratio: 1) Fulvestrant (or exemestane) + ribociclib **or** 2) Fulvestrant (or exemestane) + placebo. Fulvestrant will be given as a 500 mg dose intramuscularly (IM) every 2 weeks for 3 times (loading dose) and then every 4 weeks, as per standard of care. Exemestane will be given as 25 mg orally daily, as per standard of care. The investigational drug ribociclib will be given as 600 mg daily, 3 weeks on/1 week off. Placebo will be administered on the same schedule. For all patients, ribociclib/placebo will be supplied by the study. Fulvestrant or exemestane will be given, as standard of care.

If patient received prior fulvestrant, exemestane must be the hormone therapy backbone in the randomization. If patient received prior exemestane, fulvestrant must be the hormone therapy backbone in the randomization. If neither has been administered, selection of fulvestrant or exemestane in the randomization will be per investigator discretion.

Accrual Target: N= 120 randomized, evaluable patients. Patients will be accrued from 11 academic medical centers in the US, with a goal of completing accrual in two years.

We will ensure that neither registration scenario contains > 60% (N=80) of total study accrual.

Patients will receive treatment on study until disease progression, unacceptable toxicity, or death or withdrawal from study based on patient choice or treating physician's discretion. Every effort will be made to follow patients for primary and secondary outcomes regardless of treatment discontinuation for any reason. Crossover is not built into the study.

Evaluations

Safety Assessment:

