3. To explore differences in clinical outcome (PFS, ORR, CBR) in patients receiving an aromatase inhibitor plus ribociclib vs. palbociclib vs. abemaciclib (scenario 1), both prior to randomization and then after continuation of CDK4/6 inhibition. In addition to potential differences between clinical outcomes based on the choice of CDK4/6 inhibitor for initial treatment, there might also be differential mechanisms of resistance that could impact outcomes when CDK4/6 inhibition is continued beyond progression along with fulvestrant or exemestane. Patterns of resistance, including location of resistance, and any differences in tissue-based markers will be explored.
- **Endpoints: PFS, ORR, CBR, Site of Recurrence.** This is exploratory. Given the fact that patients with HR+ metastatic breast cancer have an improved PFS when adding CDK 4/6 inhibition to hormone therapy and given the small sample size of this study, there will not be enough patients to power this trial to evaluate the difference between CDK 4/6 inhibitors in those who register in scenario #1. Patients who received abemaciclib (LY2835219) are eligible for this trial (scenario #1).

4. To evaluate the rates of adverse events and tolerability of the combination of fulvestrant or exemestane with and without ribociclib.
 - **Endpoint: Adverse Events.** The frequency of subjects experiencing toxicities will be tabulated based upon the CTEP Active Version of the NCI Common Terminology Criteria for Adverse Events (CTCAE) v4.0.
5. To explore potential predictive tumor and blood-based predictive biomarkers.
 - **Biomarkers:** Exploratory tumor tissue biomarkers that will be examined include overexpression or amplification of Cyclin D1 and Cyclin E, phospho-Rb expression, Rb1 loss, p16^{INK4A} loss, and TK1 and TOP2A expression (as measures of E2F1 transcriptional activity). Serum and plasma will be collected and stored for potential future exploratory analyses. Differences in resistance between those who received ribociclib vs. palbociclib vs. abemaciclib will be explored.
6. To assess the impact of the combination therapy vs. fulvestrant or exemestane alone on patient reported global health assessment and quality of life.
 - **Survey Instruments.** Patient reported outcomes will be assessed using validated questionnaires (PROMIS Global Health and PROMIS 29; EQ 5D 3L)^{87,88}.

1.2.3 Summary Table of Objectives:

	Objective	Endpoint

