		^J Baseline bone scan required in all patients (whose baseline imaging is CTs of C/A/P) NOTE: If bone scan done ≤ 6 weeks prior to registration showed no evidence suggesting bone metastases and no clinical indication of skeletal pain or other evidence suggesting bone metastases, a repeat baseline bone scan is not required. If there is evidence of disease on the bone scan, bone scans should be continued every 3 cycles (~12 weeks of treatment +/- 4 days), as clinically indicated.
		^K Serum (2 red top tubes) and plasma (1 lavender tube) will be collected at each time point and stored for future potential studies. (Appendix C on collection details.) In addition, whole blood samples (2 Biocept provided tubes) will be collected and sent same day to Biocept (Appendix D).
		^L Archived tissue from primary and/or metastatic tissue is required, unless unavailable. If patient is amenable and has accessible tumor, repeat biopsy is optional. These biopsies should be considered in patients with accessible disease. Biopsies can be within 7 days of the cycle (+/- 7 days).
		^M PROMIS Global Health and PROMIS-29 and EQ-5D-3L will be performed at baseline, C4, Progression, C4b, and Off-Study. Questionnaires are not required for cycles after C4a or C4b, except Progression and Off-Study.
		^N Within 4 weeks of completing study treatment. Post-treatment follow-up every 12 weeks (+/- 1 week) for survival follow-up until study closure, which we anticipate will be up to 2.5 years after last patient enrolled (Section 6.6).
		^O Adverse event assessments every 4 weeks should include a review of concomitant medications with the patient.

10.2 Table 2: Registered After Progression on AI or tamoxifen or fulvestrant + CDK 4/6 Inhibitor (Scenario #2)

Cycle	Screen	C1D1	C1D15	C2	C2D15	C3	C4+	End of Treatment ^L
Day	-28 to -1 ^A	All pertinent assessment time points relate to Day 1 of the respective cycle +/- 4 days with the exception of scans and biopsies. ^A						
Informed consent	X							
History and Examination (incl PS) ^B	X	X	X	X		X	X	X
Adverse event assessment ^{B,N}		X	X	X		X	X	X
Fulvestrant(or exemestane)		X	X	X		X	X	
Ribociclib (or Placebo) ^C		X	X	X	X	X	X	
β-HCG (if premenopausal) ^D	X							
INR	X							
CBC, Chem7, LFTs ^E	X	X	X	X	X	X	X	X
EKG ^F	X		X	X			X	
CT C/A/P + Bone Scan (Or PET) ^{B,G,H,I}	X						X	X
Pill Diary Review			X	X		X	X	X
Blood Biomarker ^J	X			X				X
Tissue Biopsy ^K	X							X
Questionnaire ^M	X						X	X

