		^H If patients have known brain metastases and are eligible for this trial, head CT or brain MRI must be performed along with systemic imaging. If a patient does not have known brain metastases and is asymptomatic, no baseline brain imaging is required.
		^I Baseline bone scan required in all patients (whose baseline imaging is CTs of C/A/P) NOTE: If bone scan done ≤ 6 weeks prior to registration showed no evidence suggesting bone metastases and no clinical indication of skeletal pain or other evidence suggesting bone metastases, a repeat baseline bone scan is not required. If there is evidence of disease on the bone scan, bone scans should be continued every 3 cycles (~12 weeks of treatment +/- 4 days), as clinically indicated.
		^J Serum (2 red top tubes) and plasma (1 lavender tube) will be collected at each time point and stored for future potential studies. (Appendix C on collection details.). In addition, whole blood samples (2 Biocept provided tubes) will be collected and sent same day to Biocept (Appendix D).
		^K Archived tissue from primary and/or metastatic tissue is required, unless unavailable. If patient is amenable and has accessible tumor, repeat biopsy is optional. These biopsies should be considered in patients with accessible disease. Biopsies can be within 7 days of the cycle (+/- 7 days).
		^L Within 4 weeks of completing study treatment. Post-treatment follow-up every 12 weeks (+/- 1 week) for survival follow-up until study closure, which we anticipate will be up to 2.5 years after last patient enrolled (Section 6.6).
		^M PROMIS Global Health and PROMIS-29 and EQ-5D-3L will be performed at baseline, C4, and Off-Study. Questionnaires are not required for cycles after C4, except Off-Study.
		^N Adverse event assessments every 4 weeks should include a review of concomitant medications with the patient.

10.3 Table 3: Treatment Post Unblinding for Patients who were Active/On Treatment when Unblinded (Scenario #2)

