Progression-free survival will be estimated by Kaplan-Meier method and group differences between groups will be assessed using log-rank tests. Sensitivity analyses for PFS will be performed taking into consideration, but not limited to imputation of incomplete lesion measurements and study discontinuation due to progression/relapse, drug toxicity or death. Missing data patterns will be examined by summarizing the number of subjects randomized but not treated, the number of subjects who discontinued prematurely and the corresponding factors for early discontinuation. Given the potential the interval between two consecutive assessments may be longer in one arm, leading to an erroneous conclusion about differences between groups, we will perform an additional analysis (i.e. generalized log-rank) with interval censoring, especially if there is a difference in assessment schedules and considerable missing data.

Summary statistics will be calculated to describe the sample characteristics in each group. The distribution of patient responses (as defined by RECIST criteria) will be described using percentages % (n). Continuous outcomes will be summarized using mean \pm SD (standard deviation) or median (interquartile range) for non-normal data. Group comparisons will be evaluated using chi-squared or Fisher's Exact tests for categorical data and two-sided t-tests or ANOVA for continuous outcomes.

Analyses for of primary and secondary outcomes will be based on intention to treat principle, with the exception of safety endpoints, which will only be assessed in patients who receive at least one dose of treatment on study.

Subject to sample size limitations, subgroup analyses for subjects randomized to fulvestrant versus exemestane will also be considered.

All statistical analyses will be performed using SAS (version 9.4, SAS Institute Inc., Cary, North Carolina) with a type I error set at 0.05.

Sample Size Justification:

Assuming a median PFS of 3.8 months with fulvestrant alone upon progression⁸³, we predict that the addition of ribociclib to fulvestrant will lead to a median PFS of at least 6.5 months. Based upon the Evaluation of Faslodex versus Exemestane Clinical Trial (EFFECT), a randomized, double-blind, placebo-controlled, phase III trial of fulvestrant versus exemestane in patients who progressed on prior non-steroidal aromatase inhibition, the median time to progression was 3.7 months in each arm (HR=0.96, 95% CI 0.82

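### By default, patient-reported scores would be compared by t-test or ANOVA; adjusting for the score already collected before randomised treatment would be more precise

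*Combined protocol and SAP*

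**What the plan says.** Objective 6 in Section 1.2.2 is a between-arm question: "To assess the impact of the combination therapy vs. fulvestrant or exemestane alone on patient reported global health assessment and quality of life". The instruments are PROMIS Global Health, PROMIS-29 and EQ-5D-3L.

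The study calendar collects them before and after the start of randomised treatment:

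- Scenario 2 (Section 10.2, footnote M): "PROMIS Global Health and PROMIS-29 and EQ-5D-3L will be performed at baseline, C4, and Off-Study".
- Scenario 1 (Section 10.1, footnote M): "PROMIS Global Health and PROMIS-29 and EQ-5D-3L will be performed at baseline, C4, Progression, C4b, and Off-Study". Here the Progression column is progression on ribociclib plus aromatase inhibitor. It stands immediately before the post-randomisation cycles, of which C4b is the fourth.

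The statistical text of Section 13.1 compares groups by chi-squared or Fisher's exact tests for categorical data and by "two-sided t-tests or ANOVA for continuous outcomes". It mentions no baseline covariate, change score or repeated-measures model. The list of secondary endpoints in the same section, all called exploratory, does not include the questionnaires, and no questionnaire score, time point or baseline is defined for analysis.

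**The concern.** A score taken before randomised treatment is scheduled for every randomised patient, and patients who report better health before treatment will usually report better health after it. An unadjusted comparison of follow-up scores leaves that between-patient variation in the error term, and leaves any chance baseline difference between the arms in the estimate. A comparison of change scores uses the baseline, but with a fixed weight of one, which over-corrects when the correlation is moderate.

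What is at stake is the precision of the only planned comparison of quality of life between the arms. The trial is small, and fewer patients are likely to reach the Cycle 4 questionnaire than are randomised, so information that has already been collected is worth using.

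There is also a definitional gap. Baseline in Scenario 1 precedes the whole ribociclib plus aromatase inhibitor phase, whereas in Scenario 2 it comes shortly before randomised treatment. Without a rule, an analyst could pool two different quantities under one name.

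**Working it through.** The plan states no power, precision or target difference for any questionnaire, so there is no figure to reproduce.

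**Inputs from the documents**

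- Size: "N= 120 randomized, evaluable patients" (Synopsis).
- Allocation: "patients will be assigned to one of the two arms in a 1:1 ratio" (Synopsis), hence 60 per arm.
- Error rate: "with a type I error set at 0.05" (Section 13.1), taken as two-sided 0.05 for the t-tests.
- PFS medians, used only for the share of patients reaching C4: "Assuming a median PFS of 3.8 months with fulvestrant alone upon progression", and 6.5 months with ribociclib (Section 13.1).

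**Assumed, because the documents give no values**

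- Equal standard deviations at baseline and follow-up, set to 1, so differences are in SD units.
- Correlation rho between baseline and follow-up of 0.3, 0.5 or 0.7.
- For the power illustration, a true difference of 0.5 SD.

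**Formulas.** Let V = 1/n0 + 1/n1. The variance of the estimated arm difference is

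- t-test on the follow-up score: V
- t-test on change from baseline: 2(1 - rho) V
- ANCOVA on arm and baseline: (1 - rho^2) V

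ANCOVA relative to follow-up is therefore 1 - rho^2. ANCOVA relative to change is (1 - rho^2) / [2(1 - rho)] = (1 + rho)/2. The first is below 1 for any non-zero rho, the second for any rho below 1.

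**Variance ratios**

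| rho | ANCOVA / follow-up t-test | ANCOVA / change t-test | 120 patients by ANCOVA match this many by follow-up t-test |
|---|---|---|---|
| 0.3 | 0.91 | 0.65 | 120/0.91 = 132 |
| 0.5 | 0.75 | 0.75 | 120/0.75 = 160 |
| 0.7 | 0.51 | 0.85 | 120/0.51 = 235 |

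**Detectable difference at 80% power, 60 per arm.** (1.960 + 0.842) x sqrt(2/60) = 0.51 SD for the follow-up t-test. Multiplying by the square root of the relevant variance factor gives:

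| rho | Follow-up t-test | Change t-test | ANCOVA |
|---|---|---|---|
| 0.3 | 0.51 | 0.61 | 0.49 |
| 0.5 | 0.51 | 0.51 | 0.44 |
| 0.7 | 0.51 | 0.40 | 0.37 |

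**Power for a 0.5 SD difference, 60 per arm.** The follow-up t-test gives 78.2%. At rho 0.3, 0.5 and 0.7 the change t-test gives 63.9%, 78.2% and 94.2%, and ANCOVA gives 81.9%, 88.5% and 97.0%.

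**If only progression-free patients complete C4.** Day 1 of Cycle 4 falls 3 x 28 = 84 days after the start, which is 84/30.4375 = 2.76 months. With exponential PFS, exp(-ln2 x 2.76/3.8) = 0.60 of the control arm and exp(-ln2 x 2.76/6.5) = 0.75 of the ribociclib arm remain, about 36 and 45 patients. The detectable difference becomes 0.63 SD by follow-up t-test, against 0.54 SD (rho 0.5) or 0.45 SD (rho 0.7) by ANCOVA. This step shows precision only; it does not treat the selection caused by progression.

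**The case against.** The strongest reply is that the plan does not actually choose a t-test for these outcomes. The sentence in Section 13.1 closes a general paragraph that begins with describing the sample, and Section 13 never mentions PROMIS, EQ-5D or quality of life. That stands. A reader might infer that the sponsor deliberately specified an unadjusted analysis for Objective 6; the documents show only that it is the sole stated rule for continuous data, so it applies by default. EQ-5D-3L has no defined score either, and if it were analysed item by item, the categorical rule would apply. The point is therefore limited to scores treated as continuous.

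A reader might also infer that the baseline is ignored altogether, so that the saving reaches 49% at rho 0.7. The text does not say whether the outcome is the follow-up score or the change. Under the change reading the saving at rho 0.7 is 15%. ANCOVA is more precise under both readings, but the largest figure belongs to one reading only.

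Three further objections stand in part:

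- The change is not free. The current protocol version is dated February 2024, after active Scenario 2 patients were unblinded at the end of August 2023 (Section 13.6), so a new analysis rule needs a record that it was not driven by the data.
- The last score before randomised treatment is not the same measurement in the two scenarios. It is a screening score in one and a score at progression in the other, with no required interval before the randomised regimen (Section 10.1, footnote A). A scenario term is needed.
- Under the plan's own medians, about 40% and 25% of the two arms would have progressed by day 84. If progression stops completion of C4, missing scores may threaten this comparison more than lost precision does, and ANCOVA on observed scores does not cure that.

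Exploratory status limits the consequence, but gives no reason to leave collected information unused.

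**Conclusion.** The point holds as a minor improvement. The stated default is an unadjusted comparison, a score before randomised treatment is scheduled for every randomised patient, and adjusting for that score is more precise whether the default is read as a test on follow-up or on change. At assumed correlations of 0.3 to 0.7 the variance falls by 9% to 49% against the first and by 35% to 15% against the second. At rho 0.5 it falls by 25% against either, equivalent to a sample one-third larger for this endpoint (1/0.75 = 1.33).

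The direction does not depend on the assumptions, apart from rho being non-zero and below 1. The size does, because the documents give neither rho nor a standard deviation.

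It would be wrong to infer that the default analysis is biased or invalid. Randomisation makes an unadjusted comparison valid, and any bias from missing C4 scores would arise with or without adjustment. The primary PFS analysis, its error rate and the sample size are untouched.

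**What to change.** Add to the statistical analysis text of Section 13.1: *Continuous PROMIS and EQ-5D scores at C4 (Scenario 2) or C4b (Scenario 1) will be compared between arms by analysis of covariance with terms for arm, the last score before randomised treatment (screening in Scenario 2, the Progression questionnaire in Scenario 1) and registration scenario.*

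The cost is small: one or two degrees of freedom, a stated rule for patients whose baseline score is missing, and a dated note that the change was made without reference to unblinded questionnaire data. No new visits, data or patients are needed.

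The sentence does not deal with C4 scores missing because of progression, which needs its own rule, or with the Off-Study questionnaire.

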13.2 Accrual Rate

Number of Patients & Centers

The goal is to accrue approximately 150 patients across 11 different academic centers in the United States, with the expectation that each center will accrue approximately 7 patients per year over 2 years. We previously participated in a study with a similar patient population (Fulvestrant +/- Bortezomib: SABCS oral discussion 2014), with an accrual rate as above.

13.3 Evaluation of Toxicity

The frequency of subjects experiencing toxicities will be tabulated.

The case report form will be utilized for AE reporting, based upon the CTEP Active Version of the NCI Common Terminology Criteria for Adverse Events (CTCAE) v4.0.

The descriptions and grading scales in CTEP Version 4.0 of the CTCAE can be located on the CTEP website at: http://ctep.cancer.gov/protocolDevelopment/electronic_applications/ctc.htm.

All patients will be evaluable for toxicity from the time of their first treatment with the investigational drug.

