8. ADVERSE EVENTS: LIST AND REPORTING REQUIREMENTS

An Adverse Event (AE) is any undesirable sign, symptom or medical condition or experience that develops or worsens in severity after starting the first dose of study treatment or any procedure specified in the protocol, even if the event is not considered to be related to the study.

Abnormal laboratory values or diagnostic test results constitute adverse events only if they induce clinical signs or symptoms or require treatment or further diagnostic tests.

Adverse events will be monitored from the time the subject signs informed consent. Subjects will be instructed to report all AEs during the study and subjects will be assessed for the occurrence of AEs throughout the study. All AEs (serious and non-serious) must be recorded on the source documents and case report forms regardless of the assumption of a causal relationship with the study drug.

Adverse Events that begin or worsen after informed consent should be recorded in the Adverse Events section of the case report form (CRF). Conditions that were already present at the time of informed consent should be recorded in the baseline symptoms section of the CRF. Adverse Event monitoring should be continued for at least 30 days following the last dose of study treatment. Adverse Events (including lab abnormalities that constitute AEs) should be described using a diagnosis whenever possible, rather than individual underlying signs and symptoms. When a clear diagnosis cannot be identified, each sign or symptom should be reported as a separate AE.

The following list of AEs (Section 8.1) and the characteristics of an observed AE (Section 8.2) will determine whether the event requires expedited reporting **in addition** to routine reporting.

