to 1.13, $p=0.65$). Thus, this new protocol amendment allows subject to be randomized to either fulvestrant or exemestane +/- ribociclib⁶⁹, without an impact on the study design and power. A one-sided log-rank test with an overall sample size of $N=120$ randomized and evaluable subjects and with the significance level alpha set at 2.5%, achieves 80% power to detect an effect size (difference in PFS) of 3 months. We will accrue approximately 150 patients to allow for a 20% drop-out rate, non-evaluable and non-randomized subjects.

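### Toxicity is summarised only as crude subject frequencies, although time at risk depends on efficacy and could be up to about 1.5 to 1.6 times longer on ribociclib

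*Combined protocol and SAP*

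**What the plan says.** Section 13.3 states: "The frequency of subjects experiencing toxicities will be tabulated". Objective 4 in Section 1.2.2 asks about adverse events and tolerability with and without ribociclib, and names the same measure: "The frequency of subjects experiencing toxicities will be tabulated based upon the CTEP Active Version". Section 13.1 lists the adverse event rate among the exploratory secondary endpoints, with no time denominator. Its general method for categorical outcomes is: "Group comparisons will be evaluated using chi-squared or Fisher's Exact tests for categorical data".

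Sections 6.2.4 and 6.4 keep patients on treatment until progression, toxicity, death, withdrawal or investigator decision, with no limit on cycles. Section 8 adds: "Adverse Event monitoring should be continued for at least 30 days following the last dose of study treatment". AE recording starts at informed consent (Sections 8 and 8.2.14).

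The plan contains no person-time rate, time-to-first-event analysis, fixed-window table or summary of treatment duration by arm.

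**The concern.** The proportion of patients who ever have an event rises with the time they are watched. Here that time ends soon after treatment stops, and treatment usually stops at progression, which is the primary endpoint. If ribociclib delays progression as planned, its arm is watched for longer, and part of any difference in crude frequencies reflects observation time and not the drug. The distortion is largest when the trial succeeds, which is also when the tolerability comparison is most needed to weigh benefit against harm.

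The protocol recognises the mechanism elsewhere. Section 8.1 remarks that long letrozole treatment lets AEs unrelated to treatment accumulate, and it reproduces fracture rates per patient-year for arms with 562.3 and 420.9 patient-years. The same reasoning is not applied to this trial's own arms.

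**Working it through.** **Inputs.** Section 13.1 gives "Assuming a median PFS of 3.8 months with fulvestrant alone upon progression" and predicts that adding ribociclib "will lead to a median PFS of at least 6.5 months". The tail is 30 days, or 30/30.44 = 0.986 months (Section 8). Scans are about every 12 weeks, or 84/30.44 = 2.76 months (Section 13.1). The AE hazards L and the extra stopping rates below are assumptions; the documents give none.

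**The plan's own figure.** The ratio of medians is 3.8/6.5 = 0.585. For a one-sided 2.5% test with 80% power, the Schoenfeld formula needs 4(1.960 + 0.842)²/(ln 0.585)² = 109 events. With 120 patients, 24 months of accrual and an assumed minimum follow-up of 6 to 12 months, power is 0.78 to 0.81. So 3.8 and 6.5 are the medians behind the design. (The text calls the effect 3 months, whereas 6.5 − 3.8 = 2.7. That does not affect this point.)

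**Time on treatment and time at risk.** With exponential PFS and progression or death the only reason to stop, m = ln 2/median = 0.1824 and 0.1066 per month, and the mean is 1/m.
- Treatment: 5.48 vs 9.38 months, ratio 1.71.
- With the 30-day tail: 6.47 vs 10.36 months, ratio 1.60.
- If progression is found only at 12-weekly scans, the mean is 2.76/(1 − exp(−2.76m)) = 6.98 vs 10.82 months, ratio 1.55. With the tail it is 7.96 vs 11.81, ratio 1.48.
- If ribociclib patients also stop for other reasons at 2% per month, 1/(0.1066 + 0.02) = 7.90 months, and the ratio with the tail is 1.37. At 5% per month it is 6.38 months and 1.14.

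**Crude incidence of an event with the same hazard L in both arms.** With tail w, P = 1 − [m/(m + L)]·exp(−Lw). For the 12-weekly grid with step g = 2.76 and q = exp(−mg), P = 1 − exp(−Lw)·(1 − q)exp(−Lg)/(1 − q·exp(−Lg)). For extra stopping, add 0.02 or 0.05 to the ribociclib m. The tail is included throughout, and differences are taken before rounding.

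| L per month | Control vs ribociclib | Excess, points | Excess, 12-weekly grid | Excess, +2%/month stopping | Excess, +5%/month stopping |
|---|---|---|---|---|---|
| 0.02 | 11.6% vs 17.4% | 5.8 | 5.5 | 3.7 | 1.4 |
| 0.05 | 25.3% vs 35.2% | 9.9 | 9.0 | 6.5 | 2.6 |
| 0.10 | 41.5% vs 53.2% | 11.8 | 9.9 | 7.9 | 3.2 |

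With 60 per arm and a two-sided 5% test, the continuous-time excesses in the third column would be significant about 14%, 22% and 25% of the time.

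**Early windows.** If observation ends at progression, P = [L/(L + m)]·(1 − exp(−(L + m)T)). In cycle 1 (T = 28 days) with L = 0.10, this is 8.1% vs 8.4%. In the first 12 weeks with L = 0.05, it is 10.2% vs 11.2%. By week 12, 40% vs 25% have progressed or died, and mean time in the window, (1 − exp(−mT))/m, is 2.17 vs 2.39 months, a ratio of 1.10.

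**After exposure adjustment.** For a constant-hazard event unrelated to the drug, the ratio of first events per patient-month at risk is 1.00 by construction.

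**The case against.** A reader might infer that ribociclib patients will be treated 1.7 times longer and that background events will therefore pass for ribociclib toxicity. The documents do not support that strength.
- The 1.7 is a ratio of assumed PFS medians and so a ceiling on treatment time. Section 6.4 lists other reasons to stop, and Section 7.3 has many discontinuation rules for ribociclib/placebo. Time at risk for AEs, which drives the frequencies, differs less.
- The bias needs events that accrue over time. Section 8.1 describes ribociclib's characteristic effects as early: neutropenia by Day 15, and QTc change by Day 8 of the first cycle, stable or improving afterwards. Crude frequencies of these are barely affected.
- Section 13.3 itself only tabulates. The chi-squared/Fisher sentence is general and does not name AEs, secondary endpoints are called exploratory, and no efficacy or dose decision in the plan rests on the table.
- Double blinding (for on-treatment patients, until August 2023) and investigator attribution (Section 8.2.6) give partial protection.

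All of this limits the size of the problem without removing it. Blinding does not equalise observation time, AEs are recorded whatever their cause, and Section 13.3 does not restrict the table to attributed events. Objective 4 is a between-arm question, and the crude frequency is the only measure offered for it.

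**Conclusion.** The point holds as a cheap improvement to the safety analysis. Crude frequencies are a reasonable descriptive table but a poor basis for between-arm statements when observation time depends on efficacy. Under the planning medians, AE observation time could be up to about 1.5 to 1.6 times longer on ribociclib. A drug-unrelated, steadily accruing event could then show a false excess of roughly 5 to 12 points. With extra ribociclib stopping the excess is about 4 to 8 points at 2% per month and about 1 to 3 at 5% per month.

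These sizes rest on exponential PFS, the planned effect being real, and assumed constant hazards of 0.02 to 0.10 per month. If the arms have similar time on treatment, the bias vanishes. The calculation does not show that any particular event will be misattributed to ribociclib.

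**What to change.** In Section 13.3, keep the frequency table and add the following, by randomised arm and counting only post-randomisation events and time. The restriction matters because AE recording starts at consent and scenario 1 patients receive ribociclib before randomisation.
- (a) Treatment duration.
- (b) Exposure-adjusted incidence: patients with a first event per patient-month at risk, with rate ratio and 95% CI, or a time-to-first-event analysis. For patients still on treatment at the August 2023 unblinding, censor non-serious AEs at that date. Sections 6.6 and 10.3 require only SAEs and status information afterwards (including progression as a reason for stopping), so counting later months as at risk would understate non-serious rates, most in the arm with more patients still on treatment.
- (c) A table for an early fixed window: cycle 1, or the first 12 weeks with the remaining exposure difference of about 10% noted.

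State that between-arm differences will be interpreted from (b) or (c).

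The cost is a few extra safety tables. AE dates (Section 8.2.1) and dosing records (Sections 6.2 and 7) are already collected, and no procedure or sample size changes. The limitation is that (b) assumes a roughly constant hazard, which is why (c) should stand beside it for early-onset events.
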